### **2.17 Frequency of analyses**

There will be a single primary analysis when all data are entered into a database and checked for completeness and accuracy. However, our sample size calculations were based on the assumption that the SD for within-woman change during perimenopause will be 20% greater than that in menopause. Through the Data Safety and Monitoring Committee, an interim analysis when we have sufficient data for comprehensive assessment, will confirm whether this assumption was accurate; if necessary, we will increase our enrollment target to ensure we have 80% power.

### **2.18 Subgroup analysis**

We plan to do a *sensitivity analysis* of the results for those women whose pill counts show at least 80% adherence for at least 60 days of experimental treatment.

We will also perform a *subgroup analysis* for those women who meet the FDA recommended (postmenopausal) threshold for frequent, moderate-severe VMS ( $>50$  VMS/wk of  $\geq 2$  intensity).

Should our enrollment of women identifying as non-white/non-Caucasian allow it, we will assess the role of ethnicity in the effectiveness of progesterone therapy for VMS.

Participants in clinical trials may become unmasked to therapy assignment as a result of their experiences. Because, in our previous trial, women used lack of drowsiness or improved sleep to decide they were on placebo, we have explicitly stated in the consent that not all women on progesterone experience sleep changes. To address the role of expectation on the outcomes, at the final visit we will ask women whether they believe that they were randomized to the Experimental or Control therapy. This information will be used to examine the potential role of expectation on the VMS outcome.

### **2.19 Pilot data**

The experimental design is exactly parallel to a recently completed study. In that study, we enrolled 178 healthy VMS treatment-seeking postmenopausal women (1-10 years beyond their last menstrual period) into a randomized, double blind, placebo-controlled trial of daily OMP (300 mg). Secondary cardiovascular exclusions do not apply to the proposed perimenopausal study, therefore we have incorporated the observed rate of women discontinuing after randomization (20%) into our power analysis.

We also have studied 27 menstruating early perimenopausal women aged 35-50 with regular menstrual cycles and night sweats in a four-cycle observational study to pilot and validate some new questionnaires and to confirm our sample size calculations. Of these, 20 completed the entire trial (including a 1.5 cycle daily first morning urine collection). Based on this experience, we anticipate that we will enroll one woman out of each six contacts, and that 20% of enrolled

women will discontinue before study completion. Women appear most likely to discontinue prior to randomization.

### **3. Trial Management**

#### **3.1 Arrangements for day-to-day management of the trial**

A research coordinator for the study will handle the day-to-day tasks of responding to potential participants who enquire, assessing eligibility, teaching them how to complete the Calendar and interviewing them. The research coordinator will be under the direct supervision of the principal investigator and will meet with her regularly at no less than two week intervals.

When participants have completed the baseline assessment and their symptoms meet randomization criteria, they will be given a prescription for masked study medication which also has information on their Early or Late Perimenopause status. The pharmacist will access the web-based treatment allocation programme to obtain the next randomly selected allocation (see section 2.3 for details), and dispense either OMP or placebo to the participant. For remote participants, the research coordinator will go the study pharmacy on the participant's behalf and send the medication by courier.

Should there be a medical need to determine the therapy assignment for a participant during the study, [name], who is not directly involved with participants, will address any relevant clinical concerns. [name] or [name] who are also not directly involved with participants, will act as back-up in the event [name] is unavailable.

### 3.3 Trial Steering Committee and Data Safety and Monitoring Committees

All co-investigators will form the **Trial Steering Committee**—this group will meet as needed during and following the trial until the results are published and disseminated.

A **Data Safety Monitoring Committee** (DSMC) will consist of three members including a methodologist/statistician (Chair—[name], [name] at UBC) and two clinician-scientists with clinical trials experience and expertise in perimenopause and VMS (Drs. [name], Chair of Obstetrics and Gynecology at University of Colorado in Denver and [name], Associate Professor of Psychology at University of Western Ontario in London, Ontario). The DSMC will meet every six months during the trial.

## 4. Assessment of Safety

An **Adverse Event** will be defined as follows:

Any untoward medical occurrence in a participant administered a pharmaceutical product and which does not necessarily have to have a causal relationship with this treatment.

A **Serious Adverse Event** will be defined as follows:

A serious adverse event (experience) or reaction is any untoward medical

occurrence that at any dose:

- results in death,
- is life-threatening,
- requires inpatient hospitalization or prolongation of existing hospitalization,
- results in persistent or significant disability/incapacity, or
- is a congenital anomaly/birth defect .

Adverse events will be assessed throughout study participation through direct questioning of study participants, by specific study-end questionnaires and will all be followed to resolution.

All serious adverse events will be assessed by the principal investigator, reported to the DSMC and the local research ethics board, and be followed to resolution. Adverse Drug Reactions will be reported to Health Canada per applicable regulatory guidelines. For study data purposes, period of capture for serious adverse events and adverse drug reactions will be from first, up to and including last day of study treatment.

**Re: Randomized Controlled Trial of Progesterone for Perimenopausal Vasomotor Symptoms**

As Chair of the Clinical Research Ethics Board (CREB) at the University of British Columbia (UBC) that has overseen and approved the Canadian Institutes for Health Research-funded Randomized Controlled Trial of Progesterone for Perimenopausal Vasomotor Symptoms (VMS) since it began in 2011, I have reviewed the posted protocol, which was the latest one approved by CREB and the evidence that it has some inadvertent clerical omissions. I have also reviewed the proposed Amendments to this protocol.

The protocol omissions include this study's Data Safety and Monitoring Committee decision (and details about the blinded analysis leading to it) that led to the official increase in sample size. Another was that the DSMC mandated addition of the Personal Health Questionnaire-9 (PHQ-9) to screen for depression. The investigators then decided (and CREB approved) administration of the PHQ-9 also at the study end. However, the analysis of PHQ-9 was inadvertently not listed as a secondary outcome. And finally other instruments were included in the study initially for administration at the randomization and the final study visits, were approved by CREB, were partially described in the protocol but not were listed as secondary outcomes including: a likert-type assessment of "Women's Perception of Change" (related to daytime hot flushes and night sweats, flow and sleep) and the CeMCOR Perimenopause Interference Questionnaire (CeMCOR PIQ).

Although it is unusual to amend a RCT protocol once the database has been locked and statistical analysis has occurred, these amendments to the protocol are important, and they will allow the outcomes of approved, collected instruments to contribute to the scientific literature. To collect data that, for inadvertent clerical reasons cannot be evaluated and reported, would be unethical given the overall "contract" that participants make with investigators and institutions. Participants expect that what they have contributed will add to Knowledge with an expectation of providing benefit for Society or Science.

For these reasons, I approve uploading of Amendments dated November 9, 2018 to the 2014 posted protocol.

All the best,

[name]

# Amendments to Protocol—Progesterone for Perimenopausal VMS

---

These amendments are to the Progesterone for Perimenopausal VMS Protocol version 7; 12 June 2014; 09 November 2018

## **Amendment #1 (2.1 Trial Design):**

This enrolment goal was changed to 245 women based on the blinded, pre-planned interim assessment of the “effective SD” during the final month (adjusted by correlation with baseline given that they were on experimental or control therapy) after 68 women had completed the trial. (see also Amendment 6)

## **Amendment #2 (2.4 Protecting against bias)**

When it became clear that the enrolment goal had to be changed (Amendment # 1), a further year of recruitment was allowed by the Data Safety and Monitoring Committee. However, CIHR funding was not sufficient to cover this. The PI applied to Besins Healthcare International who, through the University of British Columbia and UILO agreed to and provided \$40,306.00 to fund the extension of this trial with a continued commitment to have no role in the design, conduct, analysis or publication of the study.

## **Amendment #3 (2.8 Primary and secondary outcome measures)**

The Final Questionnaire (as in the previous progesterone for menopausal RCT) included an unnamed instrument that asked several questions about overall three-month changes (decreased by up to 5 points [0 to -5] or increased by up to 5 point [0 to +5]) in VMS and in quality of sleep and characteristics of flow. This instrument is now named “Women’s Perceived Changes Questionnaire” and has become a secondary outcome.

We have also included at baseline and the final visit the CeMCOR Perimenopausal Interference Questionnaire (CeMCOR PIQ) as used in the Perimenopause Experiences Project. The within-woman body and mood changes in interference with usual activities of these two likert-type measures by therapy assignment are also a secondary outcome and will further be analyzed together as a single score.

Finally, the DSMC, partially into the RCT, recommended that we add the Personal Health Questionnaire-9 (PHQ-9) to screen out potential participants who might be depressed or suicidal. We followed their instructions but also elected to include the PHQ-9 at the Final Visit and to assess within-woman changes in the PHQ-9 score as a secondary outcome.

## **Amendment #4 (PRIMARY OUTCOME)**

We will also do subgroup analyses of VMS Score by Early Perimenopause (no skipped period or <60 day cycle length) and by Late Perimenopause (those with skipped or ≥60 day cycle lengths).

## **Amendment #5 (SECONDARY OUTCOMES)**

1. Women’s Perceived Changes Questionnaire of changes (from -5 to 0 to +5) in Daytime Hot Flushes and Nighttime Night Sweats and Hot Flushes (both number and severity) as recorded on the Final Questionnaire and by subgroup for Early and Late Perimenopause.
2. Women’s Perceived Changes Questionnaire of changes (from -5 to 0 to +5) in the quality of sleep over the three months of the trial as assessed by the Final Questionnaire based on their random assignment to the progesterone or placebo arms of this RCT and by Early/Late

## Amendments to Protocol—Progesterone for Perimenopausal VMS

---

perimenopause. (This is in addition to the listed secondary outcome: “sleep problems” from the Daily Perimenopause Diary/Perimenopause Hot Flush and Night Sweat Calendar.)

3. Within-woman changes in baseline and end-of-trial perceptions of interference of perimenopausal **body changes** and **mood changes** with usual activities (as recorded by the CeMCOR Perimenopause Interference Questionnaire [CeMCOR PIQ] at baseline and final) and in the within-woman mean of the two assessments (body and mood) scored together in women randomized to the progesterone versus to placebo and by Early/Late Perimenopause.
4. Vaginal flow (see separate Flow Study protocol) related to progesterone therapy in perimenopause will be assessed based on Women’s Perceived Changes Questionnaire of changes in the experience of menstrual flow/vaginal bleeding (-5/+5) from the Final Questionnaire, and/or change in their Diary/Calendar recorded use of sanitary products or volume of flow recorded by use of a menstrual cup compared with the same experiences in women randomized to placebo.
5. Depression related to progesterone therapy in perimenopause will be assessed based on the Personal Health Questionnaire-9 (PHQ-9) score changes within-woman from baseline to the end-of-trial compared with the women randomized to placebo.

### **Amendment #6 (2.11 Sample size)**

A pre-planned evaluation of sample size was undertaken after 68 women had completed the study. This involved evaluation of the SD of the VMS Score in the final month without regard to random study group assignment. An **effective standard deviation (SD) of ~ 9** in the Vasomotor Symptom Score SD over the last 4 weeks of experimental therapy was discovered after adjustment for the fact that the final and the run-in SD values correlated with an r of 0.56. This interim assessment was blinded and without knowledge of the therapy. The original estimated SD of 6.25 was used in our application to CIHR. This re-evaluation of sample size led to an increased enrolment of goal of 245.

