## **2.11 Sample size**

The **proposed sample size is 175 women**, to be stratified into Early and Late Perimenopause and randomized equally to active therapy or placebo. Previous analysis of similar VMS Score data from menopausal breast cancer therapy studies  concluded that a VMS Score difference of 3 is clinically important, which supports our recent estimate of 2.7 for the minimal important difference in perimenopausal women using the interpersonal assessment methods of Redelmeier  ([name] & [name], unpublished MS). This corresponds to an effect size of 0.58 . We anticipate more VMS variability in perimenopause than in postmenopause, and thus a smaller effect size. The sample size of 175 reflects an anticipated discontinuation rate of 20% (as in our past progesterone trial for VMS in postmenopausal women), and an effect size of 0.48 (revised to allow for 20% greater SD in perimenopausal women above that in postmenopause), an alpha of 0.05 using a two-tailed test and having a power of 0.80 to detect a significant difference between two groups (calculations using GPower3).

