#### **2.16 Statistical analysis**

The analysis will use analysis of covariance (ANCOVA) of the final outcome variable by therapy assignment, phase of perimenopause (Early/Late) and the interaction of therapy with phase, with baseline outcome variable as a covariate. The interaction term will assess the possibility that the response to therapy differs between those in Early and Late Perimenopause. For Daily Perimenopause Diary or Calendar VMS data, two 28-day (4-week) averages will be compared: immediately prior to therapy assignment and the final 4-weeks of the treatment phase. For questionnaires, the scores from pre-randomization and final visits will be used. The

assumptions of parametric analysis will be checked, and data will be either transformed prior to analysis or analyzed non-parametrically as required.

The primary analysis will be *intent to treat* including all women randomized and taking at least one dose of the experimental/placebo therapies with data carried forward. For practical reasons, only those with at least 14 days of Daily Perimenopause Diary or Calendar data will be included in any diary-based outcome measures (one week of baseline and one week of therapy).

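### Amendment #6: an SD of about 9 already adjusted for r = 0.56 needs about 358 women; 245 follows only if r is applied to the 9

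*Combined protocol and SAP*

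**What the plan says.** Section 2.11 sizes the trial at 175. It cites earlier work that "concluded that a VMS Score difference of 3 is clinically important", uses an effect size of 0.48, allows for 20% discontinuation, and specifies "an alpha of 0.05 using a two-tailed test and having a power of 0.80", calculated in GPower. Section 2.17 plans an interim check of the SD assumption and states the purpose: "if necessary, we will increase our enrollment target to ensure we have 80% power".

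Amendment #6 reports that check, made blinded after 68 women had completed. It gives an "effective standard deviation (SD) of ~ 9" for the final four weeks, which "was discovered after adjustment for the fact that the final and the run-in SD values correlated with an r of 0.56". It contrasts this with the 6.25 used in the grant application and concludes: "This re-evaluation of sample size led to an increased enrolment of goal of 245". Amendment #1 likewise describes the effective SD as adjusted through its correlation with baseline, without giving a value. Neither amendment restates the difference, alpha, power or dropout, and neither shows a calculation.

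**The concern.** On the plain wording, the correlation is already inside the 9. An SD that rises from 6.25 to 9 multiplies the required sample size by about (9/6.25)² = 2.07, yet the goal rises only by 245/175 = 1.40. Amendment #6 names nothing but the SD as having changed, so the stated SD and the stated goal do not fit together.

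The new goal is the result of the step that section 2.17 set up to secure 80% power. Amendment #2 ties a further year of recruitment and additional funding from the drug supplier to it. A null or borderline result has to be read against the planned power, and as written a reader cannot tell whether the 80% target was met.

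**Working it through.** **Inputs.** Difference 3, two-sided alpha 0.05, power 0.80, equal allocation and 20% loss (section 2.11); 80% power as the aim of the re-estimation (section 2.17); SD 6.25, SD about 9 and r = 0.56 (Amendment #6). Assumption: the difference, alpha, power and loss carry over unchanged to Amendment #6.

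**Method.** Two-sample t-test with the noncentral t distribution. As a guide, n per arm ≈ 2(1.96 + 0.84)² × (SD/3)²; the t-test adds about one per arm. Enrolled = analysed/0.80.

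**Reproducing 175.** 3/6.25 = 0.48. The t-test needs 69.1, so 70 per arm, and 140/0.80 = 175, as in section 2.11.

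**Same method, with about 9 taken as already adjusted:**

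| SD | Per arm | Analysed | Enrolled |
|---|---|---|---|
| 8.5 | 127 | 254 | 317.5 |
| 9 | 143 | 286 | 357.5 |
| 9.5 | 159 | 318 | 397.5 |

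Even with no loss at all, SD 8.5 needs 254 analysed, so rounding of the 9 does not reach 245. The largest SD that gives 80% power is 7.46 with 98 per arm, or 8.35 if all 245 are analysed.

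**Applying r to the 9.** The ANCOVA factor is √(1 − 0.56²) = √0.6864 = 0.8285. Then 9 × 0.8285 = 7.456 and 3/7.456 = 0.402. The t-test needs 97.94, so 98 per arm, and 196/0.80 = 245 exactly. Starting from 8.9 gives 240 and from 9.1 gives 252.5.

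**Other explanations tried:**

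- The blinded SD pools both arms. Removing a true difference of 3 gives √(81 − 2.25) = 8.87, 139 per arm, 347.5 enrolled.
- The difference of 2.7 also mentioned in section 2.11, at SD 9: 176 per arm, 440 enrolled.
- A change-score factor on 9, √(2 × (1 − 0.56)) = 0.938: SD 8.44, 126 per arm, 315 enrolled.

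**Power of 245 for a difference of 3:**

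| SD | 98 analysed per arm | All 245 analysed |
|---|---|---|
| 7.46 | 80% | 88% |
| 8.5 | 69% | 79% |
| 9 | 64% | 74% |
| 9.5 | 59% | 69% |

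The right-hand column is an upper figure, because carrying data forward may dilute the effect. With 98 per arm and SD 9, the difference detectable at 80% power is 0.4022 × 9 = 3.62.

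**What would tell the two readings apart.** If 9 is already adjusted, the unadjusted final-month SD is 9/0.8285 = 10.9 (10.3 to 11.5 for 8.5 to 9.5). If 9 is unadjusted, it is simply about 9.

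**The case against.** **The inputs are inferred.** Amendment #6 restates none of them and does not itself claim 80% power. That is correct, and 358 depends on the carry-over. But section 2.17 describes a check of the SD alone with an 80% aim, and the carried-over inputs return both 175 and, with r applied to 9, 245 exactly.

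**The route to 245 is not unique.** A difference of 3.625 (0.58 × 6.25) at SD 9, with r not applied, also gives 98 per arm and 245. This should be disclosed, but it is weak. The documents never state that difference, and it mixes inputs: 0.58 goes with an SD of 3/0.58 = 5.17, whereas 6.25 goes with 0.48.

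**The two SDs may not be the same quantity.** Section 2.17 speaks of the SD of within-woman change, while Amendment #6 concerns the final-month score adjusted for baseline. This limits a direct comparison of 6.25 with 9, but it does not alter 358.

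**The 64% is the unfavourable end.** The primary analysis in section 2.16 is described as "including all women randomized and taking at least one dose of the experimental/placebo therapies with data carried forward", subject to a minimum of 14 diary days, so more than 98 per arm may be analysed. This stands: the range at SD 9 is 64% to 74%, and at SD 8.5 with everyone analysed the shortfall is about one point.

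**It is only a record-keeping matter.** The ethics board letter says the database was locked and analysis had taken place, so enrolment cannot change, and on one reading 245 and 80% are both right. A corrected power statement would change neither the estimate nor its confidence interval. That limits what the fix can achieve. It does not remove the contradiction in the documented basis for the final sample size.

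**Conclusion.** The concern holds. Amendment #6 says r = 0.56 is already in the SD of about 9, but on the carried-over inputs its goal of 245 requires r to be applied to that 9. Taken as written, the SD calls for about 358 women (318 to 398 for SDs of 8.5 to 9.5). The arithmetic is secure; the carry-over from sections 2.11 and 2.17 is an assumption, though a well-supported one.

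Two readings remain, and the documents do not decide between them. If 9 is already adjusted, r was used twice and the 80% target was missed. If 9 is unadjusted, the effective SD is about 7.5, 245 meets the target, and only the description is wrong. Because one reading leaves the re-estimation short of its stated purpose, the text must be corrected.

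**What to change.** Look up the unadjusted final-month SD in the interim output, using the 10.9-versus-9 check. Then revise Amendment #6 to say which SD the 9 is and to list the difference, alpha, power, dropout and r behind 245.

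- **If 9 is already adjusted:** state that 245 gives about 64% power for 3 points with 98 analysed per arm (59% to 69% for SDs of 9.5 to 8.5). Add that it is at most about 74% at SD 9, or 79% at SD 8.5, if all 245 are analysed with data carried forward. Give the detectable difference at 80% power with 98 per arm as about 3.6, and say that the target in section 2.17 was not met.
- **If 9 is unadjusted:** describe it as an unadjusted SD of about 9 with an effective SD of about 7.5 after r = 0.56, and keep 245 and 80%.

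Amendment #1 gives no SD value and can stay as it is. The cost is one look at existing output and a few reworded sentences, with no new data or enrolment. On the first branch, the reported power becomes less favourable.
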